### Female Participants

Female participants of childbearing potential are eligible to participate if they agree to consistent and correct use of a highly effective method of contraception that has a low user dependency as described in [Table 17](#) during the protocol-defined time frame in Section 5.1.

Table 17 Highly Effective Contraception Methods

Contraceptives allowed during the study include:	
Highly Effective Contraceptive Methods That Have Low User Dependencya	
Failure rate of <1% per year when used consistently and correctly.	

 
• Progestogen-only subdermal contraceptive implanta,b
 
• IUSb,c
 
• Nonhormonal IUD
 
• Bilateral tubal occlusion
 
	

 
• Azoospermic partner (vasectomized or secondary to medical cause) – All sexual partner(s) of the POCBP must be azoospermic. The participant must provide verbal confirmation of partner azoospermia during Medical History. If not, an additional highly effective method of contraception should be used. A spermatogenesis cycle is approximately 90 days.
 
	
Sexual Abstinence	

 
• Sexual abstinence is considered a highly effective method only if defined as refraining from penile-vaginal intercourse with partner(s) capable of producing sperm during the entire period of risk associated with the study intervention. The reliability of sexual abstinence needs to be evaluated in relation to the duration of the study.
 
	
a If locally required, in accordance with CTFG guidelines, acceptable contraceptive implants are limited to those which inhibit ovulation.	
b If hormonal contraception efficacy for a participant assigned female sex at birth is potentially decreased due to interaction(s) with study intervention(s) (eg, CYP3A4 inducers), penile/external condoms must be used in addition to POCBP's hormonal contraception.	
c IUS is a progestin-releasing IUD.	
Note:	

 
• Male and female condoms should not be used together (due to risk of failure with friction)
 
• Tubal occlusion includes tubal ligation
 
	

**10.6 Appendix 6: Collection and Management of Specimens for Future Biomedical Research**

Not applicable.

## 10.7 Appendix 7: Country-specific Requirements

### 10.7.1 China

#### Section 1.1 Synopsis, Section 3 Hypotheses, Objectives, and Endpoints, Section 4.1 Overall Design

LEAP-003 was unblinded per an eDMC recommendation made on 27-MAR-2023. To date, there is comparatively limited data regarding the use of pembrolizumab for melanoma in China. In addition, part of the LEAP-003 China cohort was enrolled after the global study as part of a China-specific extension, resulting in shorter follow-up. For these reasons, longer data collection and follow-up of all participants enrolled in China are scientifically justified. Therefore, as of Amendment 09, additional data collection and longer follow-up according to the SoA (Section 1.3) should be done for all participants enrolled in China.

When the extended follow-up period ends at the Sponsor's discretion, but no longer than approximately 18 months from Amendment 09 approval in China, participants enrolled in China will no longer follow Section 10.7.1 and will follow activities currently outlined for the global study.

#### Section 1.1 Synopsis, Section 3 Hypotheses, Objectives, and Endpoints, Section 4.1 Overall Design, Section 6.1 Study Intervention(s) Administered, Section 6.6 Dose Modification

As of Amendment 09, the sentence "All participants beyond the 30-day Safety Follow-up Visit should be discontinued from study" does not apply to participants enrolled in China.

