### Hypotheses, Objectives, and Endpoints:

Throughout this protocol, the term Response Evaluation Criteria in Solid Tumors (RECIST 1.1) refers to the modification of RECIST 1.1 to include a maximum of 10 target lesions and a maximum of 5 target lesions per organ. Refer to Section 4.2.1.1.1 for further details.

In all participants with unresectable advanced melanoma following administration of pembrolizumab in combination with lenvatinib versus pembrolizumab in combination with placebo:

NOTE: Based on the data from an interim safety and efficacy analysis for LEAP-003 (data cutoff 18-JAN-2023), eDMC recommended stopping the study due to lack of efficacy because pembrolizumab in combination with lenvatinib did not demonstrate an improvement in OS, one of the trial's dual primary endpoints, compared to pembrolizumab plus placebo and appears unlikely to do so in a future analysis. Based upon these data and the recommendation of the eDMC, the study was unblinded as of 27-MAR-2023. The prespecified final analysis of the study described in the SAP will not be performed. Safety analysis will be performed at the end of the study; there will be no further analyses for efficacy and ePRO endpoints.

NOTE: In alignment with the study-specific investigator letter sent to investigators on 3-APR-2023, all study participants still receiving pembrolizumab should continue to receive pembrolizumab monotherapy on study and undergo modified protocol study procedures as specified in this amendment. Study participation should end after the 30-day Safety Follow-up Visit (last scheduled visit). All participants should stop ongoing treatment with lenvatinib/placebo. Exceptions may be requested for lenvatinib for study participants who, in the assessment of their study physician, are benefiting from ongoing lenvatinib after consulting with the Sponsor. This applies to participants currently on pembrolizumab and lenvatinib and participants who have completed 35 cycles of pembrolizumab and are currently continuing lenvatinib monotherapy. Participants who are considered by the investigator as candidates for continued monotherapy with lenvatinib after unblinding and completion of 35 cycles of pembrolizumab and lenvatinib require a separate communication with the Sponsor. Participants who discontinue pembrolizumab prior to completion of

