Cycle 35 (eg, due to an AE) must discontinue lenvatinib at the same time. All participants beyond the 30-day Safety Follow-up Visit should be discontinued from study; however, standard safety reporting should continue, as applicable. As of Amendment 07, participants who are still on study treatment will no longer require ePRO assessments or tumor response assessments by BICR to be performed. Scans will no longer be submitted to the iCRO. Participants who are still on study medication should continue tumor imaging assessment per protocol. For participants no longer on study medication, local tumor imaging assessments should continue per SOC schedule. Biomarker specimen collection is discontinued. The 30-day Safety Follow-up is the last required visit. Updated analyses are described in Section 9.

See Appendix 7 for country-specific requirements.

Primary Objective	Primary Endpoint
Objective: To compare progression-free survival (PFS) as assessed by blinded independent central review (BICR) per Response Evaluation Criteria in Solid Tumors (RECIST) 1.1.  Hypothesis (H1): The combination of pembrolizumab and lenvatinib is superior to pembrolizumab and placebo assessed by PFS per RECIST 1.1 by BICR.	PFS: The time from randomization to the first documented disease progression or death due to any cause, whichever occurs first
Objective: To compare the combination of pembrolizumab and lenvatinib to pembrolizumab and placebo with respect to overall survival (OS).  Hypothesis (H2): The combination of pembrolizumab and lenvatinib is superior to pembrolizumab and placebo assessed by OS.	OS: Defined as the time from date of randomization to date of death from any cause
Secondary Objectives	Secondary Endpoints
Objective: To compare objective response rate (ORR) per RECIST 1.1 by BICR.  Hypothesis (H3): The combination of pembrolizumab and lenvatinib is superior to pembrolizumab and placebo as assessed by ORR per RECIST 1.1 by BICR.	Objective response, defined as best overall response of either complete response or partial response.

Objective: To assess duration of response (DOR) per RECIST 1.1 by BICR.	DOR, determined by disease assessment defined as the time from the earliest date of qualifying response until earliest date of disease progression or death from any cause, whichever comes first.
Objective: To assess safety and tolerability.	Adverse events (AEs) Discontinuations due to AEs.

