## 1.2 Schema

The original study design is depicted in [Figure 1](#). See Appendix 7 for country-specific requirements.

Figure 1      Original Study Design

a. Prior adjuvant BRAF/MEK, PD-1 and CTLA-4 inhibitors may be allowed.

b. If End of Treatment visit occurs ~30 days from last dose of study treatment, a safety follow-up visit at 30 days is not required.

[figure not shown]
c. For participants discontinuing for reasons other than BICR-verified PD, tumor imaging should be performed Q12W, or more frequently if clinically indicated, until BICR-verified PD. If the 90 day-safety FU visit falls within the same window as the imaging FU visit, these visits may be combined.

d. Participants in Survival Follow-up will be contacted approximately Q12W or sooner to assess for survival status until death, withdrawal of consent, or the end of study, whichever occurs first.

Abbreviations: BICR = blinded independent central review; CTLA-4 = cytotoxic T lymphocyte-associated antigen 4; d = day; PD = progressive disease; PD-1 = programmed cell death 1; Q3W = every 3 weeks; Q9W = every 9 weeks; Q12W = every 12 weeks; QD = daily; RECIST = Response Evaluation Criteria in Solid Tumors.

The new study design per Amendment 07 is depicted in [Figure 2](#).

Figure 2      New Study Design

a. Prior adjuvant BRAF/MEK, PD-1 and CTLA-4 inhibitors may be allowed.

b. If End of Treatment visit occurs ~30 days from last dose of study treatment, a safety follow-up visit at 30 days is not required.

Abbreviations: BICR = blinded independent central review; CTLA-4 = cytotoxic T lymphocyte-associated antigen 4; d = day; PD = progressive disease; PD-1 = programmed cell death 1; Q3W = every 3 weeks; Q9W = every 9 weeks; Q12W = every 12 weeks; QD = daily; RECIST = Response Evaluation Criteria in Solid Tumors.

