NOTE: In alignment with the study-specific investigator letter sent to investigators on 3-APR-2023, all study participants still receiving pembrolizumab should continue to receive pembrolizumab monotherapy on study and undergo modified protocol study procedures as specified in this amendment. Study participation should end after the 30-day Safety Follow-up Visit (last scheduled visit). All participants should stop ongoing treatment with lenvatinib/placebo. Exceptions may be requested for lenvatinib for study participants who, in the assessment of their study physician, are benefiting from ongoing lenvatinib after consulting with the Sponsor. This applies to participants currently on pembrolizumab and lenvatinib and participants who have completed 35 cycles of pembrolizumab and are currently continuing lenvatinib monotherapy. Participants who are considered by the investigator as candidates for continued monotherapy with lenvatinib after unblinding and completion of 35 cycles of pembrolizumab and lenvatinib require a separate communication with the Sponsor. Participants who discontinue pembrolizumab prior to completion of Cycle 35 (eg, due to an AE) must discontinue lenvatinib at the same time. All participants beyond the 30-day Safety Follow-up Visit should be discontinued from study; however, standard safety reporting should continue, as applicable. As of Amendment 07, participants who are still on study treatment will no longer require ePRO assessments or tumor response assessments by BICR to be performed. Scans will no longer be submitted to the iCRO. Participants who are still on study medication should continue tumor imaging assessment per protocol. For participants no longer on study medication, local tumor imaging assessments should continue per SOC schedule. Biomarker specimen collection is discontinued. The 30-day Safety Follow-up is the last required visit. Updated analyses are described in Section 9.

See Appendix 7 for country-specific requirements.

Primary Objective	Primary Endpoint

Objective: To compare progression-free survival (PFS) as assessed by blinded independent central review (BICR) per Response Evaluation Criteria in Solid Tumors (RECIST) 1.1.
 
Hypothesis (H1): The combination of pembrolizumab and lenvatinib is superior to pembrolizumab and placebo assessed by PFS per RECIST 1.1 by BICR.
	
PFS: The time from randomization to the first documented disease progression or death due to any cause, whichever occurs first

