#### **4.3.3 Maximum Dose Exposure for This Study**

NOTE: In alignment with the study-specific investigator letter sent to investigators on 3-APR-2023, all study participants still receiving pembrolizumab should continue to receive pembrolizumab monotherapy on study and undergo modified protocol study procedures as specified in this amendment. Study participation should end after the 30-day Safety Follow-up Visit (last scheduled visit). All participants should stop ongoing treatment with lenvatinib/placebo. Exceptions may be requested for lenvatinib for study participants who, in the assessment of their study physician, are benefiting from ongoing lenvatinib after consulting with the Sponsor. This applies to participants currently on pembrolizumab and lenvatinib and participants who have completed 35 cycles of pembrolizumab and are currently continuing lenvatinib monotherapy. Participants who are considered by the investigator as candidates for continued monotherapy with lenvatinib after unblinding and completion of 35 cycles of pembrolizumab and lenvatinib require a separate communication with the Sponsor. Participants who discontinue pembrolizumab prior to completion of

Cycle 35 (eg, due to an AE) must discontinue lenvatinib at the same time. All participants beyond the 30-day Safety Follow-up Visit should be discontinued from study; however, standard safety reporting should continue, as applicable. As of Amendment 07, participants who are still on study treatment will no longer require ePRO assessments or tumor response assessments by BICR to be performed. Scans will no longer be submitted to the iCRO. Participants who are still on study medication should continue tumor imaging assessment per protocol. For participants no longer on study medication, local tumor imaging assessments should continue per SOC schedule. Biomarker specimen collection is discontinued. The 30-day Safety Follow-up is the last required visit. Updated analyses are described in Section 9.

The maximum dose/exposure of pembrolizumab allowed in this study is 200 mg Q3W for approximately 2 years. The maximum dose/exposure of lenvatinib allowed in this study is 20 mg QD for approximately 2 years. Participants may continue treatment with lenvatinib/placebo beyond approximately 2 years if they experience clinical benefit until unacceptable toxicity or disease progression upon Sponsor consultation and approval.

See Appendix 7 for country-specific requirements.

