### Section 1.3 Schedule of Activities

Data collection for participants enrolled in China will include all efficacy and safety evaluations per the SoA (except as noted below under "Exceptions to data collection") to support the analysis of overall survival, progression-free survival, safety, disposition, and other endpoints.

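### Does Section 10.7.1 leave China survival follow-up switched off by lifting only one of the Amendment 07 stop sentences?

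*Combined protocol and SAP*

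**What the plan says.** Amendment 07 put a block of stop wording into Sections 1.1, 3, 4.1, 4.3.3, 6.1 and 6.6. It ends participation at the 30-day safety visit and discontinues everyone beyond it. In all of these except 6.1 it adds "The 30-day Safety Follow-up is the last required visit". Separate notes in Sections 1.3, 8.1.14, 8.2.1.3, 8.11.3.2 and 8.11.4 stop follow-up scans, efficacy visits and survival follow-up.

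Amendment 09 added Section 10.7.1. For Sections 1.1, 3, 4.1, 6.1 and 6.6 it says that, from Amendment 09, "the sentence 'All participants beyond the 30-day Safety Follow-up Visit should be discontinued from study' does not apply to participants enrolled in China". It also says that "additional data collection and longer follow-up according to the SoA (Section 1.3) should be done for all participants enrolled in China", makes Figure 1 (the original design) the one that applies in China, and restores all efficacy and safety evaluations in the schedule, less a list of PRO, PK and biomarker items, "to support the analysis of overall survival, progression-free survival, safety, disposition, and other endpoints". Footnote d of Figure 1 reads: "Participants in Survival Follow-up will be contacted approximately Q12W or sooner to assess for survival status until death".

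OS is censored at last contact (Sections 9.4.1 and 9.6.1.2). The extra China data may feed supportive analyses and do not count towards the primary analysis (Section 10.7.1, entry for Section 9.9). China methods are left to the sSAP (Sections 4.1 and 9).

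**The concern.** Lifting one sentence by name invites the reading that its neighbours still bind. Section 4.3.3 makes this look worse: it contains the very sentence that is lifted and ends "See Appendix 7 for country-specific requirements", yet Section 10.7.1 has no entry for 4.3.3. The notes in 8.1.14, 8.11.3.2 and 8.11.4 carry no pointer to the appendix. The note in 8.11.4 mentions only people still on treatment at Amendment 07 for continued monitoring.

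Nor does Section 10.7.1 say what happens to China participants already discontinued when Amendment 09 was issued. Those people are mainly off treatment, and many would have progressed. If they are never traced, censoring goes with a worse prognosis and the OS curve is too high. If their deaths reach the site but survivors are not re-contacted, the curve is too low. Supporting OS is one stated purpose of the China extension, so a defect here would reach that purpose.

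**Working it through.** The plan states no figure on this point, so the check is mainly one of text.

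**What Section 10.7.1 does to each stop**

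| Stop wording | Named in 10.7.1? | What governs for China |
|---|---|---|
| Discontinue everyone beyond the 30-day visit (1.1, 3, 4.1, 6.1, 6.6) | Yes | Lifted |
| Same sentence in 4.3.3 | No | General follow-up requirement; 4.3.3 points to Appendix 7 |
| Participation ends at, or last required visit is, the 30-day visit | No | General requirement; Figure 1 replaces Figure 2 |
| Opening note of 1.3 | Not quoted, but 10.7.1 has an entry for 1.3 | All efficacy and safety evaluations restored; 1.3 points to Appendix 7 |
| Notes in 8.1.14, 8.2.1.3, 8.11.3.2, 8.11.4 | No | Schedule and Figure 1, through 10.7.1 |

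Three features settle the reading.

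1. The requirement covers all participants enrolled in China, not just those still on study or on treatment.
2. Section 10.7.1 says that when the extension ends, China participants stop following it and move to the activities outlined for the global study. That sentence makes sense only if Section 10.7.1 replaces the global outline until then.
3. Section 8.11.3.3, which sets survival contact about every 12 weeks until death, withdrawal of consent or end of study, carries no Amendment 07 note. The schedule keeps its 12-weekly survival column.

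**Participants already discontinued**

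Section 8.11.5 has no Amendment 07 note either. Once the Sponsor asks, sites contact everyone without a scheduled visit or contact in the period, which naturally describes these people. Section 8.1.1.1 covers renewed consent when new information arises.

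**The interval**

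- Amendment 07 (26-JUN-2023) to Amendment 09 (16-FEB-2024): 4 + 31 + 31 + 30 + 31 + 30 + 31 + 31 + 16 = 235 days.
- These are document dates. Appendix 1 requires regulatory and ethics approval before an amendment is implemented, and Section 10.7.1 counts its own 18 months from approval in China. No local dates are given, and nothing shows that any China participant was discontinued in the interval. Sites may instead have acted on the 3-APR-2023 letter, which would lengthen it to 319 days.

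**Illustration of size (all rates assumed)**

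Entry uniform 6 to 36 months before Amendment 07; treatment stops at 0.10 per month, capped at 24 months; death 0.01 per month on treatment and 0.05 off; follow-up to 18 months after Amendment 09. This gives 12-month OS of 73.4%, against 68.4% quoted for pembrolizumab in Section 2.2.1.4. About 61 of 130 participants would be discontinued alive before Amendment 09.

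| Handling of those discontinued | 36-month OS | Error |
|---|---|---|
| All traced | 0.247 | 0 |
| None re-entered | 0.258 | +1.1 points |
| Survivors re-enter, interim deaths missed | 0.317 | +7.0 points |
| 90% of deaths found, 50% of survivors re-contacted | 0.217 | −3.0 points |
| All deaths found, no survivor re-contacted | 0.163 | −8.4 points |

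For scale, the SE of a 50% survival estimate with 137 participants and no censoring is √(0.25/137) = 4.3 points.

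The hazard ratio stays near 1.00 in every row when the arms stop treatment alike. With unequal stopping (0.15 versus 0.08 per month) and no re-entry it moves from 1.176 to 1.274, a log shift of 0.242 − 0.162 = 0.080. With 66 events the SE of the log hazard ratio is about 2/√66 = 0.246, so the shift is about a third of one SE.

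A second set of assumptions, using the Appendix 10 PFS curve, gives errors in 24-month OS of +24 to −9 points if China enrolment ended on the Amendment 07 date, +7 to −3 if it ended 12 months before, and 0 if it ended 24 months before. The first case needs randomization to run 91 days past unblinding (27-MAR-2023) and 84 days past the letter that stopped lenvatinib/placebo, which is hard to credit.

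**The case for a change.** The strongest case is that intent is not a mechanism. A site reading 8.11.4 finds a plain instruction to stop and no pointer to the appendix. Section 10.7.1 sends the reader to Section 1.3, whose opening note says survival visits are over and whose full table is kept for reference. Vital-status requests under 8.11.5 are at the Sponsor's option, and Section 8.4.1 tells investigators that they need not actively seek events in former participants. The sSAP can set censoring rules but cannot create contacts that were never made.

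Part of this stands. The stop wording is unreconciled, 4.3.3 is missing from the list, and no sentence describes re-contact. The rest is weaker. Section 1.3 does refer to Appendix 7, whose entry for that section restores the evaluations. Section 8.4.1 concerns safety events, not vital status. The Sponsor wrote the extension partly to obtain OS, and 8.11.5 gives it the tool. A missing instruction is not evidence that people were lost. The simulated errors can exceed one SE, but only after assuming incomplete tracing that the plan does not prescribe.

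**Conclusion.** No change is called for. The omissions are clerical, together with one operational step that the Sponsor and sites can fill sensibly. A specific, later country section restores follow-up for everyone enrolled in China, and a route to vital status exists for those already off study. A fuller list of superseded notes would read better but would leave the same people followed at the same times.

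The effect on the supportive China OS cannot be determined: it may be upward, downward or nil. It is nil with complete tracing, or if the risk of death is unrelated to treatment status. At most 137 participants are concerned, and the global primary analysis is unaffected.

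This rests on two assumptions: sites follow Section 10.7.1 over the general Amendment 07 notes, and the Sponsor uses Section 8.11.5 for discontinued participants, dead or alive. The sSAP was not available and may already set the handling.
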